7 INTERVENTION ARM

7.1 Intervention Arm Medication Alert Intervention Description

Randomized providers at each site will be informed in advance of the quality improvement study being conducted. The communication will inform intervention arm providers of the nature of the interventional components (e.g., medication alert, case review by a child and adolescent psychiatrist, behavioral health navigation, bridging therapy).

The medication alert is triggered by entering an antipsychotic in Epic for a target patient. See Appendix B. The patient is added to a study enrollment log at the time of the encounter. The intervention arm medication alert links providers to a document containing *Choosing Wisely*[®] guidelines, the national expert consensus panel clinical guidelines developed for SUAY, and contextual study information.

Within the alert, the prescriber has the option to:

- keep/remove the medication entered (default = remove)
- keep/remove an order for a provider-to-provider consult with the CAP (default = keep)
- keep/remove an order for BH navigation for the patient (default = keep)
- keep/remove an order for expedited access to bridging therapy for the patient (default = keep)

The study CAP is automatically notified that a review is needed each time an intervention arm provider actively orders a CAP review in the alert and after a patient is verified eligible when a consult is not actively ordered.

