We will compare the outcomes of patients initially prescribed an antipsychotic medication from intervention providers versus control providers. We plan to conduct an intent-to-treat analysis i.e. if a patient is enrolled when an intervention provider issues a qualifying prescription, the patient is enrolled in the intervention arm and, even if the patient sees a control provider at some point, the patient will remain in the intervention arm. Intervention arm is a binary treatment assignment that should be indicated for all enrolled patients in the analytic dataset.

Baseline Covariates

Baseline covariates for this study include: age, gender, race, ethnicity, site, type of insurance (Medicaid/Commercial/Other i.e. self-paid), any inpatient hospitalization in the prior year, provider type and new health plan enrollee (defined as person who does not have 2 or more encounters at least 60 days apart in the year prior to their prescription order date). This definition of new health plan enrollee will be compared to an alternate definition in the three sites with health plan enrollment data: < 105 days enrolled in the health care plan before randomization date). Note that gaps in enrollment less than 45 days count towards the total of 105. Gaps in enrollment ≥ 45 days do not count towards the total of 105, nor does any enrollment prior to the gap ≥ 45 days. Any inpatient hospitalization in the prior year (-1 to -365 days from randomization date) will be adjusted for in primary analyses as it is prognostic of the outcome and will increase precision.

Health plan enrollment and follow-up time

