Definition I: BMI/laboratory measure/orders at baseline is defined as BMI/laboratory measure/orders observed in the 90 days before randomization and 7 days after randomization. BMI/laboratory during follow-up is defined as any BMI/laboratory measure/orders observed at least 30 days to +181 days following the randomization date. If no AP orders were made on the randomization date then these variables should be NA. The main predictor is the treatment arm (intervention or control). For these analyses, we will exclude those that did not have an AP order on randomization date.

We will perform 3 logistic regression analysis, where the outcome is a binary indicator of

- i. BMI/Laboratory measure/orders entered at baseline (yes/no)
- ii. BMI/Laboratory measure/orders entered at follow-up (yes/no)
- iii. BMI/Laboratory measure/orders entered at baseline and follow-up (yes/no)

For these analyses, we will exclude those that did not have an AP order on randomization date.

Descriptive analysis will summarize **the percent of patients with observed BMI/Laboratory measure/orders at i, ii or iii**, defined above. For these analyses, we will exclude those that did not have an AP order on randomization date.

Inferential analysis: We will estimate the **odds ratio (OR) of BMI/Laboratory measure/orders observed at i or ii or iii**, between intervention and control. Binary treatment arm assignment will be the only covariate included in the regression model and the estimated coefficient is interpreted as the log-OR of observing BMI/Laboratory measure/orders at i or ii or iii, for an intervention patient vs. a control patient. Patient is the unit of analysis, GEE will be used to account for correlation within provider, and robust standard errors will be calculated to construct a 95% CI around the estimated OR. Our null hypothesis is that the OR is equal to 1, corresponding to no statistically significant difference between BMI/Laboratory measure/orders observed at i or ii or iii, for the treatment arms. We will reject the null hypothesis if the lower bound of the 95% CI is above 1 (increased BMI/Laboratory

Analysis plan for Safety Use of Antipsychotics in Youth (SUAY)

measure/orders in treatment arm) or the upper bound is below 1 (decreased BMI/Laboratory measure/orders in treatment arm). For these analyses, we will exclude those that did not have an AP order on randomization date.

Variables	Definition	Present/Absent

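### Secondary analysis II is the SAP's only patient-level arm comparison without a baseline covariate, and its follow-up model leaves out earlier recording of the same measure, at some cost in power

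*SAP*

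**What the plan says.** SAP, Secondary analysis II, fits three logistic models for each of BMI, lipids, cholesterol, HbA1c, prolactin and any laboratory test: (i) recorded at baseline, (ii) recorded at follow-up, (iii) "BMI/Laboratory measure/orders entered at baseline and follow-up (yes/no"). For all three, "Binary treatment arm assignment will be the only covariate included in the regression model". The variable table for this section has no prior-hospitalization variable, so the omission is not a slip in one sentence.

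Baseline means "BMI/laboratory measure/orders observed in the 90 days before randomization and 7 days after randomization". Follow-up means "any BMI/laboratory measure/orders observed at least 30 days to +181 days following the randomization date". The analysis set is restricted: "we will exclude those that did not have an AP order on randomization date".

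Under Baseline Covariates, the SAP says that prior-year hospitalization "will be adjusted for in primary analyses as it is prognostic of the outcome and will increase precision". That sentence covers the primary analyses. The secondary models for ED and urgent care visits, treatment change and therapy attendance carry the same covariate all the same.

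**The concern.** Patients whose clinicians recorded BMI or ordered laboratory tests before the alert are likely to have them recorded afterwards too. Model ii is also the monitoring outcome on which the intervention acts most directly: Protocol 7.4 has the navigator remind families of laboratory tests due three months after an antipsychotic is started, which falls inside the day 30 to 181 window. Leaving out a likely strong predictor costs power there, and leaves any chance imbalance in earlier monitoring inside the arm comparison. Such imbalance is plausible, because providers are the units randomized and Protocol 5.3.1 notes that at one site a few of them wrote a large share of the qualifying prescriptions.

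**Working it through.** **1. Covariates in each SAP model**

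| Analysis | Unit | Covariates |
|---|---|---|
| Primary I, Primary II | patient | arm + prior hospitalization |
| Secondary I, III, VII | patient | arm + prior hospitalization |
| Secondary II (i, ii, iii) | patient | arm only |
| Secondary IV, V, VI | none | descriptive only |
| Secondary VIII | provider | arm only; SAP notes it was not conducted |

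Secondary II is therefore the only patient-level comparison of arms without a baseline covariate. Earlier recording enters as outcome i and as part of outcome iii. Only model ii makes no use of it.

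**2. Size of the loss in model ii**

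The plan states no power, rate or standard error for Secondary II, so there is no figure to reproduce. Assumed inputs, none from the documents: n = 300 per arm, 40% of controls monitored at follow-up, 35% of patients with the measure recorded earlier, conditional treatment odds ratio (OR) 1.6, and a baseline OR (earlier recording to later recording) of 2, 3 or 5. Power is Φ(log-OR / SE − 1.96).

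Worked case, baseline OR 3:
- Controls: 57.1% monitored if recorded earlier, 30.8% if not; 0.35 × 0.571 + 0.65 × 0.308 = 0.40.
- Intervention (odds × 1.6): 68.1% and 41.6%; 0.35 × 0.681 + 0.65 × 0.416 = 0.508.
- Arm only: marginal OR = (0.508/0.492)/(0.40/0.60) = 1.55, log-OR 0.439. SE = √[1/(300 × 0.508 × 0.492) + 1/(300 × 0.40 × 0.60)] = 0.165. Power = Φ(2.66 − 1.96) = 76%.
- Adjusted: each stratum has information 1/[1/(n₁p₁(1−p₁)) + 1/(n₀p₀(1−p₀))], with 105 per arm recorded earlier and 195 not. This gives 12.09 + 22.13 = 34.22, so SE = 1/√34.22 = 0.171. Log 1.6 = 0.470. Power = Φ(2.75 − 1.96) = 79%.

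| Baseline OR | Marginal OR | SE, arm only | SE, adjusted | Power, arm only | Power, adjusted |
|---|---|---|---|---|---|
| 2 | 1.58 | 0.165 | 0.167 | 79% | 80% |
| 3 | 1.55 | 0.165 | 0.171 | 76% | 79% |
| 5 | 1.50 | 0.165 | 0.178 | 69% | 75% |

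The SE of the log-OR rises slightly. Power rises because the conditional OR (1.60) lies further from 1 than the marginal OR.

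**3. Other assumptions**

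With 360 per arm (the protocol's upper limit at 6 months), 40% v 50% monitored, half recorded earlier, and correlation phi between earlier and later recording:

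| phi | Arm-only power | Adjusted power | Fall in variance, standardized log-OR |
|---|---|---|---|
| 0.1 | 76.8% | 77.2% | 1% |
| 0.2 | 76.8% | 78.4% | 4% |
| 0.3 | 76.8% | 80.6% | 9% |
| 0.5 | 76.8% | 87.5% | 26% |

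A simulation with clustering (120 providers of 6 patients, independence GEE, sandwich SE) moved power from 67% to 71% at phi about 0.17, and from about 55% to 68% at phi about 0.38. For a covariate like prior hospitalization (assumed 20% prevalence, phi 0.05 to 0.2) the gain was 0.1 to 1.5 points.

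**4. Why the SAP's baseline variables cannot be the covariate**

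The SAP's window runs to day +7. Protocol Appendix A puts the alert on day 0 and targets psychiatrist review for days 0 to 6, so arm can change recording in days 0 to +7. In the simulation, if the intervention raised testing in those days by an assumed 30 points with no true follow-up effect, adjusting for the -90 to +7 variable gave a log-OR of -0.09 to -0.22 and a type I error of 8.5% to 22%.

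**The case against.** The case against is fair in several respects.

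- *No rule is broken.* A reader might infer that the SAP breaches its own commitment to adjust. It does not: the precision rationale is written for the primary analyses, and nothing in the documents says that hospitalization predicts BMI or laboratory monitoring. What stands is an unexplained inconsistency among the secondary models.
- *The standard error is not inflated.* A reader might infer that the unadjusted OR is needlessly imprecise. In logistic regression, adjustment does not generally shrink the SE of the log-OR, as the first power table shows. The gain is in power, or in precision if a standardized effect is estimated.
- *The predictor is not ready-made.* The SAP's table marks every monitoring variable in this section as absent. The -90 to +7 definition does, however, require the records for days -90 to -1.
- *The strength of the predictor is assumed.* Eligible patients generally have no outpatient antipsychotic order in the prior 180 days, so earlier testing need not reflect antipsychotic monitoring. The correlation could be low, and the gain with it.
- *The change is not free.* The OR in model ii becomes conditional and no longer matches models i and iii. The other SAP models already report covariate-adjusted ratios, so this is a matter of labelling. The SAP also records that age differs significantly by arm, so some data had been examined, and a covariate added now may be post hoc.

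A reader might also infer that adjustment would repair selection. The analysis set needs an antipsychotic order on the randomization date, while the intervention alert lets the prescriber "keep/remove the medication entered (default = remove"). The arms may therefore differ in who is retained. A covariate can reduce measured imbalance, but the documents do not support calling it a cure for that selection.

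**Conclusion.** The point holds as a minor improvement. Secondary II alone among the patient-level arm comparisons has no baseline covariate, without a stated reason, and model ii leaves out a likely predictor. The loss is about 1 to 6 power points under the first set of assumptions. Over the wider range it is about 0.4 to 4 points for phi 0.1 to 0.3 and about 11 points at phi 0.5, with 360 per arm. All of this rests on assumed sample sizes, testing rates, treatment effects and associations. Prior hospitalization is worth adding for consistency, with little expected gain. The arm-only analysis is not shown to be invalid; it is less powerful than it could be.

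**What to change.** In model ii, add an indicator that the same measure was recorded in days -90 to -1, built from the records already needed for the SAP's baseline definition. Do not use the -90 to +7 variables as covariates. Add prior_hosp, already listed as present for the other models, to all Secondary II models.

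Costs to state in the SAP:
- An indicator must be derived for each measure.
- The OR in model ii becomes conditional, so report the arm-only or a standardized estimate beside it.
- If outcome data have been seen, label the adjusted model a sensitivity analysis.

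One caution: the SAP's randomization date is the day the alert fires for the patient, whereas Protocol 5.3.1 assigns providers before the trial starts. Days -90 to -1 precede this patient's alert, but a provider's earlier alerts could have changed testing habits in that window. This is a further reason to keep the arm-only result in view.

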5.3.3 Cross-Over Prevention Procedures

Epic coding will ensure control arm providers cannot access intervention components. Periodic checks will be conducted to ensure this remains in place as planned.

If a control arm provider reaches out for a consultation, the CAP may still discuss treatment options and make recommendations as they would as part of their normal role.

The behavioral health navigator will be responsible for ensuring that the services s/he offers and the bridging therapy are only accessible to intervention arm patients and providers.

Patients who change to the panel of a provider assigned to a different arm during the 6 month follow-up period will remain in the arm of their original prescriber for the 6 month follow up period.

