7.5 Short-Term Bridging Therapy Description

Either the study CAP or the prescribing clinician may decline bridging therapy for the subject based on the clinical scenario. The BH navigator will use a decision tree to further assess appropriateness of short-term bridging therapy. Any reason that bridging is not offered will be noted in the navigator's reporting workbench (e.g., declined by prescriber, CAP advised against, subject already engaged in therapy, etc.).

The BH navigator will administer modified oral consent/assent for bridging services, as required by the local IRB, schedule the initial session, and note if the teen/family requires a loaner device (e.g., tablet) if bridging visits are to be delivered via telemental health (TMH) video visits.

When TMH is to be delivered, a TMH privacy and safety plan with the subject prior to the first TMH session. The offer of TMH will be suspended if a privacy or safety concern is identified when the form is completed until a clinical decision can be made by the therapist. The plan identifies resources within and outside the home to ensure patient privacy during TMH sessions, and plan for any potential crises, safety concerns, or inability to contact the teen/family.

All bridging visits will be entered in Epic as patient visits. There will be no copays or other charges billed for these study-related visits.

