10.1.1 Safe Practice Protocols and Tracking

BH navigators will have contact with intervention arm patients/families and will follow safe practice protocol if a patient or parent/guardian voluntarily discloses thoughts of self-harm. Study navigators do not assess suicide risk directly. See Appendix D of this protocol.

Safe practice protocol use, actions taken, and resolution for each event will be tracked and summarized in reports for DSMB. The events will not be considered adverse events because there is no comparison data from the control arm.

The study therapists are members of the local health system workforce and therefore follow their health system's clinical protocols if thoughts of self-harm are reported by a patient.

In addition to safe practice protocols, both navigators and therapists are mandatory reporters. Standard procedures for reporting to Child Protective Services (CPS) will be followed should a subject voluntarily disclose child neglect or abuse. CPS reporting will not be tracked for study purposes.

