groupn	Randomization Group - use for descriptive stats (Intervention (1)/Control(2))	present
group_cat	Randomization Group - use in models (Control (0)/Intervention (1))	present
bmi_baseline	0 = no, 1 = yes, 8 = NA	absent
bmi_fu	0 = no, 1 = yes, 8 = NA	absent
bmi_both	If bmi_baseline AND bmi_fu = 1, then 1 = yes, otherwise 0 = no; if no AP order on randomization date, then 8 = NA.	absent
lipids_baseline	0 = no, 1 = yes, 8 = NA	absent
lipids_fu	0 = no, 1 = yes, 8 = NA	absent
lipids_both	If lipids_baseline AND lipids_fu = 1, then 1 = yes, otherwise 0 = no; if no AP order on randomization date, then 8 = NA.	absent
chl_baseline	0 = no, 1 = yes, 8 = NA	absent
chl_fu	0 = no, 1 = yes, 8 = NA	absent
chl_both	If chl_baseline AND chl_fu = 1, then 1 = yes, otherwise 0 = no; if no AP order on randomization date, then 8 = NA.	absent
hb1ac_baseline	0 = no, 1 = yes, 8 = NA	absent
hb1ac_fu	0 = no, 1 = yes, 8 = NA	absent
hb1ac_both	If hb1ac_baseline AND hb1ac_fu = 1, then 1 = yes, otherwise 0 = no; if no AP order on randomization date, then 8 = NA.	absent
prolactin_baseline	0 = no, 1 = yes, 8 = NA	absent
prolactin_fu	0 = no, 1 = yes, 8 = NA	absent
prolactin_both	If prolactin_baseline AND prolactin_fu = 1, then 1 = yes, otherwise 0 = no; if no AP order on randomization date, then 8=NA.	absent
any_lab_baseline	0 = no, 1 = yes, 8 = NA	absent
any_lab_fu	0 = no, 1 = yes, 8 = NA	absent
any_lab_both	If any_lab_baseline AND any_lab_fu = 1, then 1 = yes, otherwise 0 = no; if no AP order on randomization date, then 8=NA.	absent

Secondary analysis III

Percentage of clinicians with at least one change in AP treatment (defined as AP discontinuation, treatment adjustment (change in other psychotropic medication), and therapy referral);

Definition: At least one of the following must occur to be flagged as 'Yes' or assigned the number 1

- AP discontinuation: no refills
- Medication adjustment i.e. non-AP mental health adjustment (either of the two below or both) by provider within 60 days of patient enrollment in study:
 - adding new psychotropic medication (including switching medications)
- Therapy referral by provider within 60 days of patient enrollment in study.
 - any new psychotherapy i.e. referral
- New mental health diagnosis (issued by the same provider) within 60 days of patient enrollment in study.

Analysis plan for Safety Use of Antipsychotics in Youth (SUAY)

- At least one AP treatment change

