Descriptive analysis will summarize **the percent of** clinicians with each type of change and at least one change in AP treatment (AP discontinuation, treatment adjustment, therapy referral, and new diagnosis), defined above.

Inferential analysis: We will estimate the **odds ratio (OR) of at least one change in AP treatment**, between intervention and control. Binary treatment arm assignment and prior hospitalization will be the only covariate included in the regression model and the estimated coefficient is interpreted as the log-OR of observing at least one change in AP treatment, for an intervention patient vs. a control patient. Patient is the unit of analysis, GEE will be used to account for correlation within provider, and robust standard errors will be calculated to construct a 95% CI around the estimated OR. Our null hypothesis is that the OR is equal to 1, corresponding to no statistically significant difference between the AP treatment, for the treatment arms. We will reject the null hypothesis if the lower bound of the 95% CI is above 1 (increased change in AP treatment in treatment arm) or the upper bound is below 1 (decreased change in AP treatment in treatment arm).

Variables	Definition	Present/Absent
groupn	Randomization Group – use for descriptive stats (Intervention (1)/Control(2))	present
group_cat	Randomization Group – use in models (Control (0)/Intervention (1))	present
prior_hosp	Prior Hospitalization (No (0)/Yes(1))	present
no_refill	if there exists a rdate < rxdate for AP <= enddate or disenrollmentdate, then 0 = no, otherwise 1=yes	absent
new_med	0 = no new medication within [rdate, rdate + 60 days], 1 = at least one new medication within [rdate, rdate + 60 days]	absent
th_referral	0 = no new psychotherapy visit observed within [rdate, rdate + 60 days], Otherwise, 1 = at least one new psychotherapy visit	absent
new_mh_dx	0 = no new mental health diagnosis, 1 = at least one new mental health diagnosis	absent
trt_change	If no_refills, new_med, th_referral, and new_mh_dx = 0, 0 = no AP treatment change, Otherwise 1 = at least one AP treatment change	absent

Secondary analysis IV

Modal stage at departure from algorithm (first line, second line, third line treatment prior to antipsychotic);

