Percentage of patients attending two or more system-provided therapy sessions

Descriptive analysis will summarize **the percent of patients attending two or more system-provided therapy sessions**

Inferential analysis: We will estimate the **odds ratio (OR) of attendance to two or more system-provided therapy sessions between intervention and control.** The outcome will be

Analysis plan for Safety Use of Antipsychotics in Youth (SUAY)

binary: two or more sessions (outcome=1) vs. fewer than two sessions (outcome=0). Binary treatment arm assignment and prior hospitalizations will be the only covariate included in the regression model and the estimated coefficient is interpreted as the log-OR of attending two or more system-provided therapy sessions, for an intervention patient vs. a control patient. Patient is the unit of analysis, GEE will be used to account for correlation within provider, and robust standard errors will be calculated to construct a 95% CI around the estimated OR. Our null hypothesis is that the OR is equal to 1, corresponding to no statistically significant difference between attending system-provided sessions, for the treatment arms. We will reject the null hypothesis if the lower bound of the 95% CI is above 1 (increased attendance to two or more system-provided therapy sessions in treatment arm) or the upper bound is below 1 (decreased attendance to two or more system-provided therapy sessions, in treatment arm).

Variables	Definition	Present/Absent
groupn	Randomization Group – use for descriptive stats (Intervention (1)/Control(2))	present
group_cat	Randomization Group – use in models (Control (0)/Intervention (1))	present
prior_hosp	Prior Hospitalization (No (0)/Yes(1))	present
th_sessions	defined as patients attending at least 2 system-provided therapy sessions (visits) throughout the study period	present

Secondary analysis VIII

Note: Data harvesting was not completed and this analysis was not conducted due to time constraints.

- (i) Behavioral Change Analysis: Proportion of providers’ patients with any AP order after BPA exposure during the study
- (ii) Sustainment Analysis: Proportion of providers’ patients with any AP order, both during and after the study

Note that: Intervention BPA gets turns off and Control Arm BPA turns on for both groups (July 1, 2020)

Behavioral Change Analysis:

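### Secondary analysis III codes a provider's therapy referral as any new psychotherapy visit, so study bridging visits, open to one arm only, can count as clinician treatment change

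*SAP*

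**What the plan says.** The definition list in SAP Secondary analysis III includes "Therapy referral by provider within 60 days of patient enrollment in study". A sub-item directly beneath it explains this as any new psychotherapy. The variable table then codes `th_referral` from visits. The value 0 is "0 = no new psychotherapy visit observed within [rdate, rdate + 60 days", and the other value is "Otherwise, 1 = at least one new psychotherapy visit". The coding requires no referral and no link to the enrolling provider, and it does not say whether study sessions count.

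The composite is positive if any component is: "If no_refills, new_med, th_referral, and new_mh_dx = 0, 0 = no AP treatment change", and 1 otherwise. The arms are compared on this composite by an OR with a 95% confidence interval. An interval wholly above 1 is to be read as more change in antipsychotic treatment in the intervention arm. The single components are only summarised descriptively.

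The protocol says of the study's bridging therapy:

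- Section 7.5: "All bridging visits will be entered in Epic as patient visits".
- Section 5.3.3: the navigator must ensure that navigation services and "the bridging therapy are only accessible to intervention arm patients and providers". Section 6 adds that a control provider who tries to order a study service is told the patient is not eligible.
- Summary, description of intervention: bridging is meant for families not already engaged in psychotherapy.
- Section 7.1: in the intervention alert, the bridging order is kept by default.
- Section 7.4: where no study service was ordered, the navigator still contacts the family unless the provider declines.
- Appendix A: family outreach has a target start of day 6.

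**The concern.** Secondary analysis III is meant to show whether clinicians changed treatment after the alert. A bridging session is a component of the intervention. If it counts as the outcome, the analysis partly compares an arm that was given the service with an arm that was barred from it. The OR then mixes two things: what prescribers did, and whether the study delivered its own therapy. A reader of the result could not tell them apart, and the SAP's planned interpretation attributes the whole difference to treatment change.

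**Working it through.** The documents give no rate, power or effect size for this outcome, so there is no planned figure to reproduce. The check has two steps.

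**Step 1: does a bridging visit meet the coded definition?**

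- It is a psychotherapy visit and it is recorded in Epic (Protocol 7.5).
- It is likely to be new, because bridging is aimed at youth not in psychotherapy (Protocol summary).
- It can fall within 60 days, because outreach is targeted from day 6 (Appendix A).
- No exclusion of study visits appears in the `th_referral` row of the SAP.
- It cannot occur in the control arm if the access controls work (Protocol 5.3.3 and 6).

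So it can set `th_referral`, and through it `trt_change`, to 1 in the intervention arm only.

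**Step 2: how far could this move the tested OR?**

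Let p0 be the probability that `trt_change` = 1 apart from bridging, equal in both arms (no other intervention effect). Let b be the share of intervention patients with no other flagged change who have a bridging visit within 60 days. Both are assumptions. Then

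- p1 = p0 + (1 − p0)·b
- OR = [p1/(1 − p1)] / [p0/(1 − p0)]

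With p0 = 0.60 the control odds are 0.60/0.40 = 1.50:

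- b = 0.10: p1 = 0.60 + 0.40 × 0.10 = 0.64; OR = (0.64/0.36)/1.50 = 1.19
- b = 0.20: p1 = 0.68; OR = (0.68/0.32)/1.50 = 1.42
- b = 0.30: p1 = 0.72; OR = (0.72/0.28)/1.50 = 1.71

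For the chance of declaring a difference, take n = 400 per arm (the upper figure in Protocol 8.1) and a two-sided 0.05 level, with no clustering or covariates:

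P(reject) = Φ{ [(p1 − p0) − 1.96·√(2p̄(1 − p̄)/n)] / √([p0(1 − p0) + p1(1 − p1)]/n) }, where p̄ = (p0 + p1)/2.

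Example with p0 = 0.60 and b = 0.20: p̄ = 0.64, the first root is 0.03394 and the second 0.03382, so (0.08 − 0.0665)/0.03382 = 0.398 and P(reject) = 65%.

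| p0 | OR at b = 0.10 / 0.20 / 0.30 | P(reject) at b = 0.10 / 0.20 / 0.30 |
|---|---|---|
| 0.30 | 1.37 / 1.83 / 2.43 | 56% / 99% / >99% |
| 0.50 | 1.22 / 1.50 / 1.86 | 29% / 81% / 99% |
| 0.60 | 1.19 / 1.42 / 1.71 | 21% / 65% / 95% |
| 0.70 | 1.16 / 1.36 / 1.61 | 15% / 48% / 83% |

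The nominal rate is 5%. Clustering within provider would lower these probabilities but would not remove the shift in the OR. The shift shrinks as the other components become more common. With bridging excluded, b = 0, p1 = p0 and the OR is 1.

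**The case against.** The best case for the plan has several parts.

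- **The SAP glosses referral as new psychotherapy.** This stands in part. It makes the gap between text and code narrower than a flat contradiction. It does not settle whether study sessions count, and the outcome is still labelled and interpreted as clinician change.
- **Some bridging follows a prescriber's order.** This also stands in part. A provider who leaves the bridging order in the alert has placed an order, and a provider may decline bridging. A reader might infer that the whole excess would arise with prescribers doing nothing, and the documents do not support that. Only visits reached through navigator outreach without an order fit that description cleanly. But the order is itself a study component that control prescribers cannot place, so the imbalance between arms remains.
- **The variable is not yet built.** `th_referral` and `trt_change` are marked absent, so a restriction could be added when they are derived. That is true, and it is why the SAP should say so now. The bias follows from applying the text as written; it is not shown to have occurred.

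Two stronger readings are tempting but not supported. First, one might infer that `th_sessions` in Secondary analysis VII has the same fault, because "The study therapists are members of the local health system workforce". It is, however, "defined as patients attending at least 2 system-provided therapy sessions (visits) throughout the study period", and Protocol 3.2 lists system-provided and study-provided sessions as separate outcomes. System-provided therefore already means something other than bridging. Second, one might infer that a new mental health diagnosis does not belong in the composite. The heading and the outcome list leave it out, but the definition list, the descriptive text and the coding all include it. That is a labelling mismatch, and removing the component would be a matter of preference.

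**Conclusion.** The point holds for `th_referral` and, through it, for the tested composite `trt_change`. As written, the coding lets a service confined to one arm count as the outcome. It biases the OR upward as a measure of clinician treatment change. The direction follows from the definitions and the access rules, provided some intervention patients with no other flagged change attend bridging within 60 days. The size is unknown: 1.19 to 1.71 is an illustration that assumes a 60% base, 10% to 30% uptake among otherwise-unflagged patients, equal base rates and no other effect. ORs for `th_referral` alone would correspond to no planned test. The outcome is secondary and neither primary outcome is touched, but the correction is worth making before the variable is derived.

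**What to change.** State in Secondary analysis III that study bridging does not count, by one of two routes:

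1. Limit `th_referral` to new system-provided psychotherapy visits within 60 days, matching Secondary analysis VII, by excluding bridging visits with a study therapist as identified in Epic.
2. Code it from the enrolling provider's referral orders to system therapy, with the study bridging order explicitly excluded. Without that exclusion this route would not cure the problem, because the order is kept by default in the intervention alert and blocked in the control arm.

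Either way, report bridging visits separately and descriptively for the intervention arm.

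The cost is SAP wording and a data filter, with some classification work. Visits or orders must be marked as study or system. The telemental health session count in Secondary analysis V is not enough for this: it carries no dates, the therapists' metrics go into a de-identified database (Protocol 14.2), and bridging may also be by phone or in person (Protocol 7.5.1). Route 2 misses referrals made outside Epic. Route 1 misses referrals that produce no visit within 60 days, and it still counts system visits that a navigator arranged, so route 2 is closer to clinician behaviour.
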